10.3 Population for Analysis

The following populations will be considered for the analyses:

- Intention to treat (ITT) population: All randomized participants will be included in the main ITT analyses, regardless of protocol adherence.
- Per-protocol population (PP): Includes all patients in the ITT population having completed the study treatment without major protocol violations and good adherence to the IMP.

Criteria for inclusion in the PP population will be specified in the SAP and the final criteria will be defined prior to database lock

- Safety population: Includes all subjects with any safety information after baseline. Patients randomized to Remdesivir without receiving any amount of the treatment will be excluded from the safety population.
- Total population: All enrolled participants independent of study arm will be used for additional analyses in the total population.

The primary population is the ITT population.

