The Investigational NOR-SOLIDARITY protocol

[figure not shown]
Project title

The NOR Solidarity multicenter trial on the efficacy of different anti-viral drugs in SARS-CoV-2 infected patients

Short title: The NOR-SOLIDARITY trial

EudraCT no: 2020-000982-18

Version: 12 2020-06-11

CONFIDENTIAL

This document is confidential and the property of the study group. No part of it may be transmitted, reproduced, published, or used without prior written authorisation.

STATEMENT OF COMPLIANCE

This document is a protocol for a clinical research study. The study will be conducted in compliance with all stipulations of this protocol, the conditions of Regional Ethic committee approval and the latest version of the Helsinki Declaration.

This protocol describes a multicenter add-on trial that is part of and based on the global WHO COVID-19 core protocol. The aim of the WHO COVID-19 core protocol is to evaluate and compare four different antiviral treatment regimens on in-hospital mortality in moderate and severe COVID infected patients. This multicenter add-on trial will be a separate and independent trial but will use the global level randomization and contribute to report endpoints and adverse events to the global trial.

Synopsis of the protocol

Terminology: The novel coronavirus-induced disease first described in 2019 in China is designated COVID-19 (or COVID), and the pathogen itself (an RNA virus) is SARS-coronavirus-2 (SARS-CoV-2). The Norwegian study that is an adapted WHO-study and follows the WHO protocol whilst also analyzing additional factors is referred to as the NOR-SOLIDARITY study. Standard of Care will be referred to as SoC.

Background: In early 2020 there were no approved anti-viral treatments for COVID, and WHO expert groups advised that four re-purposed drugs, Hydroxychloroquine, Remdesivir, Lopinavir with Ritonavir and Interferon (β 1a) should be evaluated in an international five-arm randomized trial where the fifth arm is SoC. The NOR-SOLIDARITY study started analyzing the effects of Hydroxychloroquine and Remdesivir initially and may open for a fourth arm.

Notification: Hydroxychloroquine was removed as treatment option by the steering committee on June 8th 2020 due to lack of evidence confirmed both in internal WHO interim analyses and an external report from the Recovery study. Thus, from this date, June 8th 2020, NOR-Solidarity allocate patients only to SoC and SoC+ Remdesivir.

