Patient enrolment and randomization: This will be carried out online via a database created for this purpose by the WHO. Adults (age \geq 18 years) recently hospitalized, or already in hospital, with definite COVID and, in the view of the responsible doctor, no contra-indication to any of the study drugs will be randomly allocated between

- Local SoC alone,
OR local SoC plus
- Remdesivir

Data reported before randomization via the WHO database:

- Hospital and randomizing doctor
- Confirmation that informed consent has been obtained
- Patient identifiers, age and sex
- Patient characteristics (yes/no): current smoking, diabetes, heart disease, chronic lung disease, chronic liver disease, asthma, HIV infection, active tuberculosis.
- COVID-19 severity at entry (yes/no): shortness of breath, being given oxygen, already on a ventilator, and, if lungs imaged, major bilateral abnormality (infiltrations/patchy shadowing)
- Whether the study drug is currently NOT AVAILABLE at the hospital.

Inclusion criteria

1. Adult patients, 18 years and older
2. Confirmed SARS-CoV-2 infection by PCR
3. Admitted to the hospital ward or the ICU
4. Subjects (or legally authorized representative) provide informed consent prior to initiation of the study
5. No anticipated transfer within 72 hours to a non-study hospital

Exclusion criteria

1. Severe co-morbidity with life expectancy $<$ 3 months according to investigators assessment
2. ASAT/ALAT $>$ 5 times the upper limit of normal
3. Acute co-morbidity within 7 days before inclusion such as myocardial infarction
4. Known intolerance to the study drug
5. Pregnancy or breast feeding
6. Any reason why, in the opinion of the investigators, the patient should not participate

7. Participation in a potentially confounding drug or device trial during the course of the study
8. Already receiving any of the current study drug(s)
9. Patients on concomitant medications, which is part of the list of prohibited medications have to be excluded from the current study.

Prohibited medication:

Haloperidol, carbamazepine, phenytoin, rifampin, phenobarbital, isoniazid, pyrazinamide, nevirapine, ritonavir, sodium valproate/valproic acid

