5.1 Remdesivir

The lyophilized formulation of Remdesivir is a preservative-free, white to off-white or yellow, lyophilized solid containing 100 mg of Remdesivir to be reconstituted with 19 ml sterile water for injection and diluted with IV infusion fluids prior to IV infusion. It is supplied as a sterile product in a single-use, 50 mL, Type 1 clear glass vial. Following reconstitution, each vial contains 5 mg/ ml concentrated Remdesivir solution with sufficient volume to allow withdrawal of 20 ml (100 mg of Remdesivir). In addition to the active ingredient, the lyophilized formulation of Remdesivir contains the following inactive ingredients: water for injection, SBECD (sulfobutylether cyclodextrin), hydrochloric acid, and/or sodium hydroxide. Hydrochloric acid and/or sodium hydroxide are used to adjust the formulation to a final pH of 3.0 to 4.0 following reconstitution.

Remdesivir will be delivered by WHO when available. Remdesivir will be given intravenously with a loading dose of 200 mg at inclusion, day 1. Thereafter the patient will receive a daily intravenous maintenance dose of 100 mg from day 2 to day 10.

The total volume of administration can be 250 mL or 500 mL of Normal Saline. The infusion can be administered over a period of between 30 minutes and 2 hours.

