10.2 Randomization

10.2.1 Allocation- sequence generation

Eligible patients will be allocated in an equal ratio, using a computer randomization procedure. The allocation sequence will be prepared by an independent statistician appointed by the international steering group. The randomization procedure will accommodate availability of each treatment such that a patient cannot be allocated to an unavailable treatment. There will be no stratification of the allocation sequence, only simple randomization.

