10.2.2 Allocation- procedure to randomize a patient

Eligible patients will be entered into the www.who.int/COVIDcore database including patient baseline details and available treatment arms at the study site. Patients will then be randomized to one of the available arms. The allocation will be registered in the patient's journal and in the eCRF system (Viedoc). This is an open-label study and no steps to conceal allocation are necessary. The study statistician will be blinded to the randomization allocation for the writing of the national statistical analysis plan (SAP). The authorisations bound to role of the study statistician in the eCRF when reading or downloading data will ensure that the statistician won't see the treatment allocation until database lock.

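### The ITT set ignores remdesivir availability, so standard-of-care patients who could not have been allocated to remdesivir can enter its comparison

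*Protocol*

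**What the plan says.** Protocol section 10.3 defines the ITT population thus: "All randomized participants will be included in the main ITT analyses, regardless of protocol adherence". It adds that "The primary population is the ITT population". In that section only the per-protocol criteria are left to the SAP.

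Allocation is conditional on supply. Section 10.2.1: "The randomization procedure will accommodate availability of each treatment such that a patient cannot be allocated to an unavailable treatment". Section 10.2.2: "Patients will then be randomized to one of the available arms". Section 5.1 makes supply uncertain: "Remdesivir will be delivered by WHO when available". Among the items the Synopsis lists for entry before randomisation is "Whether the study drug is currently NOT AVAILABLE at the hospital".

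The set of arms has changed. The Synopsis background says: "The NOR-SOLIDARITY study started analyzing the effects of Hydroxychloroquine and Remdesivir initially and may open for a fourth arm". Its notification says: "Thus, from this date, June 8th 2020, NOR-Solidarity allocate patients only to SoC and SoC+ Remdesivir".

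Section 10.5.1 takes the primary mortality analysis from the WHO core protocol and its analysis plan, applied to this trial's population and split by severity at entry. Section 10.5.2 analyses secondary efficacy endpoints on the ITT and per-protocol populations. Section 10.1 sizes the trial on receipt of intensive care, a secondary endpoint, at 406 per group. Section 10.4 uses 406 per arm as the recruitment goal that can trigger the analysis.

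**The concern.** An ITT analysis is protected because every patient in the comparison could have been allocated to either arm. While hydroxychloroquine was open, an SoC patient at a site without remdesivir was randomised, but against hydroxychloroquine only. The chance of allocation to remdesivir was zero. Section 10.3 still includes that patient, and nothing elsewhere in the protocol limits the controls for remdesivir to patients who could have received it.

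Such controls come from particular sites and an earlier period. SoC is local, and allocation is simple and unstratified, so differences in case mix, admission practice or background care pass into the treatment estimate. The count of 406 per arm is affected too: it does not separate comparable from non-comparable controls.

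**Working it through.** **Plan's own figure.** Inputs from section 10.1: ICU rate 70/268 = 26%, difference 10 points (so 16% on treatment), two-sided 2.5%, power 90%. With unpooled variance,

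n = (2.2414 + 1.2816)² × (0.26×0.74 + 0.16×0.84) / 0.10² = 12.411 × 0.3268 / 0.01 = 405.6, so 406 per group.

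The stated figure reproduces.

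**Who can be allocated to what.**

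| Period | Remdesivir at site | Hydroxychloroquine at site | Arms open besides SoC | SoC patient comparable with remdesivir? |
|---|---|---|---|---|
| Before 8 June 2020 | yes | yes or no | remdesivir, with or without hydroxychloroquine | yes |
| Before 8 June 2020 | no | yes | hydroxychloroquine only | no, yet randomised and so in ITT |
| From 8 June 2020 | yes | arm closed | remdesivir | yes |
| From 8 June 2020 | no | arm closed | none | not stated whether entered |

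The second row carries the point.

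**Size of the bias.** The documents give neither the share w of SoC patients entered without remdesivir nor the difference d between their ICU risk and that of other controls. Both are assumed here. Under no treatment effect, with 406 per arm:

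- spurious difference = w × d
- SE = √(2 × 0.26 × 0.74 / 406) = 0.0308
- type I error = Φ(−2.2414 + wd/SE) + Φ(−2.2414 − wd/SE)

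| w | d | w × d | wd/SE | Type I error (nominal 2.5%) |
|---|---|---|---|---|
| any | 0 | 0 | 0 | 2.5% |
| 10% | 5 points | 0.5 points | 0.162 | 2.7% |
| 20% | 10 points | 2 points | 0.650 | 5.8% |
| 30% | 10 points | 3 points | 0.974 | 10.3% |

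Letting the control variance follow the shifted control rate changes little: 10.0% to 10.7% in the last row, depending on the sign of d. In that row, power for a true 10-point effect would be 61% if the extra controls have the lower risk (16%) and 99% if they have the higher risk (36%). It is 89.7% with no shift (test with pooled variance under the null).

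**Power after restriction.** With 406 on remdesivir and the non-comparable controls removed from 406 without replacement, by the same pooled-variance calculation:

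| Controls removed | Controls left | Power, 26% v 16% |
|---|---|---|
| none | 406 | 89.7% |
| 10% | 365 | 88.0% |
| 30% | 284 | 83.2% |

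These losses are pessimistic. Section 10.2.1 allocates in equal ratio among available arms, so comparable controls should be about as many as remdesivir patients. Once remdesivir reaches 406, about 406 comparable controls are expected.

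**The case against.** Four arguments deserve weight.

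1. **The ITT sentence is standard and concerns adherence.** It defines a population, not the control group for one contrast. Taken literally it would also admit hydroxychloroquine patients, which nobody intends. This stands in part: the protocol never says outright that all SoC patients are compared with remdesivir. But the sentence is the only definition of the main analysis set, and its literal breadth shows that the contrast needs its own definition.

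2. **The control group may be fixed elsewhere.** The WHO core plan governs the primary mortality analysis and may already restrict controls. This stands for mortality, so a reader should not infer that the primary analysis is shown to be biased. It is weaker for receipt of intensive care, where section 10.5.2 follows the primary method only where applicable and uses this protocol's populations. If the WHO plan does restrict controls, section 10.3 is out of step with it.

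3. **After 8 June 2020.** A reader might infer that patients are entered on SoC without any random draw whenever remdesivir is missing. The documents do not say so. The ITT set covers randomised patients, the availability field may serve to prevent such entries, and section 10.3 distinguishes randomised from enrolled patients. The protocol is merely silent.

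4. **Other protection.** It would be too strong to say there is none. The split by severity at entry in 10.5.1 and the regression or Mantel-Haenszel options in 10.5.2 can remove part of a case-mix difference. Neither is specified to handle site or calendar time.

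**Conclusion.** The point holds for SoC patients randomised before 8 June 2020 at sites without remdesivir. The protocol's allocation rule and its ITT definition do not fit together for the remdesivir comparison, and the endpoint on which the trial is sized depends on that definition.

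The size is unknown. Under the assumptions shown, type I error runs from 2.7%, which is negligible, to 10.3%, which is not; with equal risks there is no bias. These figures concern receipt of intensive care, and no figure is derived for mortality. The documents do not report that any site actually lacked remdesivir, only that supply was conditional. The sponsor can count the affected patients from the availability field.

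**What to change.** - In 10.3 and 10.5, define the remdesivir comparison as patients for whom remdesivir was recorded as available at randomisation and who were allocated to remdesivir or SoC, analysed by allocation.
- In 10.1 and 10.4, count the 406 per arm within that set.
- In 10.2, state that a patient for whom SoC is the only available arm is not counted as randomised in this comparison.
- In 10.5.1, confirm that the control definition agrees with the WHO core plan.

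This remains an intention-to-treat analysis, because availability is recorded before allocation. Within the restricted set the remdesivir to SoC ratio is equal whether or not hydroxychloroquine was also open, so the confounding of site and calendar time with arm is removed.

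The cost is a sentence or so in each section and no new data. Some SoC patients leave this comparison: power would be about 88% if 10% of 406 controls are removed and about 83% if 30% are, without replacement. Counting the 406 within the restricted set avoids that loss but may lengthen recruitment. The change should be made before the statistician sees allocation, so that the choice of controls cannot depend on results.

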2.3 Study design

The NOR-SOLIDARITY study is an adaptive, randomized, open clinical multicentre trial to evaluate the safety and efficacy of possible therapeutic agents in hospitalized adult patients diagnosed with COVID-19. See the WHO COVID-19 core protocol (Appendix 1) for the core trial design. This multicentre add-on trial will follow the WHO core protocol version 10 dated 22.03.2020 but will add additional secondary and exploratory endpoints.

Adults (age ≥ 18 years) recently hospitalized, or already in hospital, with definite COVID and, in the view of the responsible doctor, no contra-indication to any of the study drugs will be randomly allocated between

- Local standard of care alone,
OR local standard of care plus
- Remdesivir (one intravenous loading dose, then daily infusions for altogether 10 days)

The primary objective of the trial is to investigate the effect of Remdesivir on all-cause in-hospital mortality compared to standard of care.

Patients will be followed daily during hospitalization, after 28 days by telephone/sms and then by an outpatient clinical visit after 3 months.

In the core protocol follow-up data are only collected at discharge. In this protocol subjects will additionally be assessed for efficacy and safety both during hospitalization and after hospitalization.

In addition to the global independent data and safety monitoring board (DSMB) as described in the core protocol, a national DSMB will monitor the safety and risk-benefit of the trial interventions in the Norwegian population.

[figure not shown]

Figure 2: The Investigational NOR-SOLIDARITY protocol

3 Objectives and endpoints

Objectives	Endpoints (Outcome measures)
Primary (in line with WHO core protocol)	
To investigate the effect of Remdesivir on all-cause in-hospital mortality compared to standard care.	All-cause in-hospital mortality
Secondary (in line with WHO core protocol)	
Assess the effect of Remdesivir on hospital duration, receipt of ventilation or intensive care, and to identify any serious adverse reactions.	During hospitalization 
 • Receipt of mechanical ventilation • Time to first receiving and duration of mechanical ventilation • Receipt of intensive care • Duration of intensive care • Occurrence of Suspected Unexpected Serious Adverse Reactions (SUSARs)
Secondary (as addition to the WHO core protocol)	

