9.4 Protocol deviations

A protocol deviation handling plan will describe reporting procedures for important protocol deviations. Substantial overdosing should be reported within 24 hours in the WHO study website. As the protocol leaves the local doctor fully responsible for all decisions about patient care, including the possibility of discontinuing study medication if this is considered appropriate, the

only possible major protocol deviation would be substantial over-dosing with a study drug. If this happens, it should be reported within 24 hours on the study website. The DSMC chair will then decide whether this constitutes a sufficiently major protocol deviation for it to need to be forwarded promptly to the relevant national coordinator and to any relevant ethics committee

10 Statistical methods and data analysis

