10.5.2 Secondary analyses

Between group comparisons will be performed for the primary variable on the per-protocol population in addition to secondary efficacy endpoints on both efficacy populations (ITT and PP populations).

The between-group comparisons for secondary variables will be tested as for the primary variable where applicable and additional analyses will be performed based on the following methods (but not limited to):

- Continuous secondary variables will be subject to repeated measures mixed models or appropriate non-parametric alternatives
- Binary response variables will be analysed using logistic regression (possibly adjusting for within-subject dependencies by generalized estimating equations or mixed models) or chi-square/Mantel-Haenszel tests
- Time-to-event variables will be analysed using the Kaplan-Meier method and comparisons between the two groups will be performed using the log rank test, Cox regression analyses or appropriate parametric models such as the gamma or Weibull model.

Unless otherwise specified, all statistical hypotheses will be tested as the primary variable, i.e. with an assessment of superiority of the estimated difference between the groups. All efficacy analyses will be presented with the results from the hypothesis testing (by p-value) in addition to estimates and 95% confidence limits of the treatment effect.

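### The per-protocol population in section 10.3 depends on completing a course that only the remdesivir arm has, so the supportive per-protocol comparisons suffer one-arm, outcome-related selection of unknown net direction

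*Protocol*

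**What the plan says.** Section 10.3 of the protocol gives the PP rule: "Includes all patients in the ITT population having completed the study treatment without major protocol violations and good adherence to the IMP". The next sentence reads "Criteria for inclusion in the PP population will be specified in the SAP and the final criteria will be defined prior to database lock", and the section ends by stating "The primary population is the ITT population".

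The treatment to be completed is set out in section 2.3 as "Remdesivir (one intravenous loading dose, then daily infusions for altogether 10 days", and in section 5.1, after the day 1 loading dose, as "Thereafter the patient will receive a daily intravenous maintenance dose of 100 mg from day 2 to day 10". The comparator in section 2.3 is "Local standard of care alone".

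Section 10.5.2 then uses the set for efficacy: "Between group comparisons will be performed for the primary variable on the per-protocol population". It adds the secondary efficacy endpoints on both the intention-to-treat (ITT) and PP populations. These include receipt of intensive care, the endpoint on which section 10.1 bases the national target of 406 per group.

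On deviations, section 9.4 says the "only possible major protocol deviation would be substantial over-dosing with a study drug". Sections 6 and 9.4 also allow study drug to be stopped while the patient remains in the study.

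**The concern.** Completion and adherence to the investigational product are conditions that a standard-care patient cannot fail. A remdesivir patient who dies on day 5 has not completed treatment and leaves PP; a standard-care patient who dies on day 5 stays. The same holds for a patient discharged on day 5, and for one whose drug is stopped in a way the protocol permits.

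Membership therefore depends on what happens after randomisation, in one arm only, and what happens is closely tied to the endpoints compared. A drug with no effect can show a PP difference in mortality or in intensive care. At stake is whether the PP results can be read as support for, or a challenge to, the ITT result. The protocol states no exception for early death or discharge.

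**Working it through.** **Inputs from the protocol, section 10.1.** Control in-hospital mortality p = 5%; clinically meaningful difference 2 points; intensive care 26%, with a 10-point difference; 406 per group.

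**Check of those inputs.** With the unpooled normal approximation, n = (z₀.₉₈₇₅ + z₀.₉₀)² × [p₁(1−p₁) + p₂(1−p₂)] / (p₁−p₂)², and (2.2414 + 1.2816)² = 12.411.
- Mortality, 5% v 3%: 12.411 × 0.0766 / 0.0004 = 2377, as stated.
- Intensive care, 26% v 16%: 12.411 × 0.3268 / 0.01 = 406, as stated.

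The protocol gives no figure for the PP set, so the rest is a no-effect model.

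**Assumptions not in the documents.** f is the share of remdesivir deaths that occur before completion, and g is the share of remdesivir survivors who do not complete. All control patients stay in PP, and both arms have the same true mortality p.

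**Formula.** Remdesivir PP mortality is q = p(1−f) / [p(1−f) + (1−p)(1−g)]. Dividing its odds by p/(1−p) gives the PP odds ratio under no effect: (1−f)/(1−g). It is below 1 when f > g, equal to 1 when f = g, and above 1 when g > f.

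**Mortality.** The first results column keeps early discharges (g = 0). The other two also drop 30% or 50% of non-ICU patients, all alive: 0.74 × 0.30 = 0.222 of the arm (g = 0.222/0.95 = 23.4%) or 0.74 × 0.50 = 0.370 (g = 38.9%).

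| f | g = 0 | 30% of non-ICU dropped | 50% of non-ICU dropped |
|---|---|---|---|
| 40% | 0.030/0.980 = 3.06% | 0.030/0.758 = 3.96% | 0.030/0.610 = 4.92% |
| 60% | 0.020/0.970 = 2.06% | 0.020/0.748 = 2.67% | 0.020/0.600 = 3.33% |
| 70% | 0.015/0.965 = 1.55% | 0.015/0.743 = 2.02% | 0.015/0.595 = 2.52% |

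Control is 5.0% throughout. The spurious gain is 1.9 to 3.4 points if only early deaths leave, and 0.1 to 3.0 points if early discharges leave too.

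**Reversal.** At f = 50%:
- g = 25% gives 3.4% (odds ratio 0.67);
- g = 50% gives 5.0% (odds ratio 1.00);
- g = 75% gives 0.025/(0.025 + 0.2375) = 9.5% (odds ratio 2.00), against the drug.

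**False conclusions in the one-sided case.** With g = 0, 406 randomised per arm and the 2.5% two-sided level of section 10.1, the chance of a significant PP mortality benefit from an inert drug is about 8%, 33% and 77% for f = 25%, 50% and 75%. The nominal chance is 1.25%.

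**Intensive care.** Dropping 30% or 50% of non-ICU patients for early discharge raises receipt on remdesivir from 26% to 0.26/(0.26 + 0.518) = 33.4% or 0.26/(0.26 + 0.370) = 41.3%, with no drug effect. If early deaths also leave and all of them are ICU patients, 40–70% early deaths remove 0.020–0.035 of the arm. The range then becomes 0.225/(0.225 + 0.518) = 30.3% to 0.240/(0.240 + 0.370) = 39.3%, still above 26%.

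**The case against.** The strongest reply is that section 10.3 leaves the PP criteria to the SAP and their final form to a date before database lock. How completion treats death or discharge before day 10 is ordinary SAP detail, and the SAP was not among the documents available here. This stands in part: the SAP can still repair the point. But the protocol does more than defer. It states completion and adherence as the rule. A SAP that follows the rule keeps the selection, and one that counts early deaths and discharges as adherent departs from the protocol's wording.

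Second, ITT is primary, the PP mortality comparison is listed only among secondary analyses, and section 10.1 relies on the combined global analyses for mortality. This stands fully. No primary conclusion rests on PP.

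Third, a reader might infer that the PP mortality comparison is simply biased towards remdesivir. The documents do not support that. It requires completion to be read literally for deaths but set aside for discharges. Read consistently, both groups leave, the two pulls oppose each other, and the protocol gives neither share.

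Fourth, a reader might infer from section 9.4 that no exclusion could ever fall on standard care. That overreads a passage about reporting deviations. Section 9.4 also refers to a separate plan for important deviations, section 10.3 speaks of violations, and the SAP could define ineligibility or receipt of remdesivir on standard care as exclusions. What remains is a mismatch of terms that should be aligned.

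**Conclusion.** The point holds for the PP definition as written: membership depends on a post-randomisation, outcome-related condition that only one arm can fail, and mortality and secondary endpoints are to be compared on that set. The asymmetry follows from the text alone.

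The size and net direction do not. They rest on assumed shares of early deaths and early non-completion among survivors. Within the ranges shown, the distortion in mortality runs from almost nothing to more than the 2 points that section 10.1 calls clinically meaningful, and it can reverse. For intensive care, the early-discharge assumptions used put the distortion against the drug. A comparison whose bias has unknown sign cannot serve as support.

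Severity is moderate. A reader might infer that the trial's main result is compromised; it is not, because the primary analysis is ITT and the PP criteria are not yet final.

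**What to change.** Before database lock, replace the completion condition in section 10.3, and carry the same text into the SAP, with criteria that can apply to both arms:

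- Both arms: eligible patients who started the allocated strategy and followed it for as long as they were alive and in hospital.
- Patients who were adherent until death or discharge before day 10 stay in PP.
- Standard care: no remdesivir received.
- State how patients whose study drug is stopped as sections 6 and 9.4 allow are classified. Excluding them would still be a one-arm exclusion, so PP should be reported as supportive either way.
- Use one term for major violations or deviations in sections 10.3 and 9.4, with one meaning.

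The cost is one definition in the protocol and SAP. The rule relies on dates of dosing, death and discharge and on drug received, so no extra data are needed. No change to dosing or to any clinical rule is implied.

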9.1.7 Time Period and Frequency for Event Assessment and Follow-Up

For this study, all Grade 3 and 4 AEs, Grade 1 and 2 AEs for Remdesivir occurring while administration or within the first hour and all SAEs occurring from the time the informed consent is signed through three months follow-up will be documented, recorded, and reported.

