10.2.3 Blinding and emergency unblinding

This is an open-label study. However, the staff at the central laboratory at OUS as well as the statistician responsible for analysis of the data will be blinded to the treatment allocation for the writing of the SAP.

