10.5.3 Safety analyses

Safety endpoints include death through three months, SAEs, discontinuation of study infusions, and severe AEs. These events will be analysed univariately and as a composite endpoint. Time-to-event methods will be used for death and the composite endpoint. Each AE will be counted once for a given participant and graded by severity and relationship to COVID-19 or study intervention. AEs will be coded using the current version of the Medical Dictionary for Regulatory Activities (MedDRA). AEs will be presented by system organ class, duration (in days), start- and stop-date. Adverse events leading to premature discontinuation from the study intervention and serious treatment-emergent AEs should be presented either in a table or a listing.

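### The safety population drops never-dosed remdesivir patients with no counterpart under standard care, so a between-arm comparison of deaths and SAEs in that set is selective, in a direction not known in advance

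*Protocol*

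**What the plan says.** Protocol section 10.3 builds the safety population in two steps. The general rule, and the only one that applies to standard care, reads: "Includes all subjects with any safety information after baseline". The second step touches one arm: "Patients randomized to Remdesivir without receiving any amount of the treatment will be excluded from the safety population". The section leaves the per-protocol criteria to the SAP but states this rule outright.

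Section 10.5.3 lists the endpoints: "Safety endpoints include death through three months, SAEs, discontinuation of study infusions, and severe AEs". They are analysed one by one and as a composite. On method it says: "Time-to-event methods will be used for death and the composite endpoint". It gives neither the analysis population nor the time origin.

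Section 9.1.7 requires recording of "all SAEs occurring from the time the informed consent is signed through three months follow-up", so events before a first infusion are collected in both arms. On timing of treatment, section 5.1 says: "Remdesivir will be given intravenously with a loading dose of 200 mg at inclusion, day 1". On blinding, section 10.2.3 says: "This is an open-label study". Section 2.3 makes local standard of care alone the comparator.

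**The concern.** A dosed-only safety set is balanced when each arm starts a product. Here, membership depends on an event after randomisation that can occur in only one arm. A remdesivir patient who dies before the first infusion leaves the set. A standard-care patient with the same course stays, provided some post-baseline safety information exists. The same applies to a remdesivir patient who has SAEs or severe AEs and is never dosed.

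Never-dosed patients need not be a random subset. Section 6 lets patients stop study treatment and stay in the study. Section 9.4 leaves decisions on study medication to the local doctor, who knows the allocation. The reasons for no dose may therefore be related to prognosis.

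At stake are the results for which the protocol states no intention-to-treat analysis: death through three months, SAEs, severe AEs and the composite.

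**Working it through.** **Inputs from the protocol (section 10.1).** 406 patients per arm; 5% in-hospital mortality under standard care. The 406 reproduces with the unpooled two-proportion formula for 26% against 16%, two-sided 2.5%, 90% power:

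(2.2414 + 1.2816)² × (0.26×0.74 + 0.16×0.84) / 0.10² = 12.41 × 0.3268 / 0.01 = 405.6, so 406.

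**Assumptions.** The protocol does not give the share never dosed, *u*, or mortality among them, *d*, so both are varied. The 5% is the in-hospital figure and stands in for three-month mortality, which is not given.

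**Formula.** With true mortality *p* in both arms (no drug effect), the remdesivir rate seen in the safety population is (p − u·d)/(1 − u). Dividing by *p* gives the risk ratio (RR) that would appear. With all randomised patients kept, each arm shows 20.3/406 = 5.0% and the RR is 1.00.

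**Apparent RR when the true RR is 1.00, p = 5%:**

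| Never dosed | d = 0% | d = 5% | d = 20% | d = 50% |
|---|---|---|---|---|
| 1% (about 4) | 1.01 | 1.00 | 0.97 | 0.91 |
| 2% (about 8) | 1.02 | 1.00 | 0.94 | 0.82 |
| 5% (about 20) | 1.05 | 1.00 | 0.84 | 0.53 |

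Worked cells:
- u = 2%, d = 20%: (0.05 − 0.004)/0.98 = 4.69%, RR 0.94.
- u = 5%, d = 20%: (0.05 − 0.010)/0.95 = 4.21%, RR 0.84.
- u = 2%, d = 50%: (0.05 − 0.010)/0.98 = 4.08%, RR 0.82. About 4 of 20 deaths leave the arm.
- u = 5%, d = 0%: 0.05/0.95 = 5.26%, RR 1.05.

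The 0.53 corner would need half of all remdesivir deaths (10.15 of 20.3) to fall among about 20 never-dosed patients. The conclusion does not rely on it.

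**Higher background mortality.** At p = 10%, u = 2%, d = 50%: (0.10 − 0.01)/0.98 = 9.18%, RR 0.92. The distortion shrinks as *d* comes closer to *p*.

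**What could be masked.** For the safety set to show 5% in both arms, true remdesivir mortality would be 0.05(1 − u) + u·d. With u = 2%, d = 50% this is 0.049 + 0.010 = 5.9%, a true RR of 1.18. With u = 1%, d = 50% it is 5.45%, a true RR of 1.09.

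**Against chance.** With 20.3 expected deaths per arm, the standard error of log RR is √[2 × (1/20.3 − 1/406)] = 0.31. The shift to 0.82 is 0.20 on the log scale, and the shift to 0.94 is 0.06.

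The same formula holds for SAEs or severe AEs with their own rates. The protocol gives none, so no figure is offered.

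**The case against.** The strongest reply is that little may turn on this. The first dose is planned at inclusion. Section 10.2.1 prevents allocation to an unavailable treatment, and section 4.1 bars patients with an anticipated transfer to a non-study hospital within 72 hours. The never-dosed group may be very small. In-hospital mortality is the primary endpoint in all randomised patients, and 28-day survival is a secondary endpoint analysed on ITT as well as per protocol (sections 3, 10.3, 10.5.1, 10.5.2), so early deaths remain visible. The plausible shifts are below one standard error of log RR. A dosed-only set also has a purpose: an event in a never-dosed patient is not a drug effect, and adding such patients dilutes true drug-related events. All of this stands and limits the weight of the point. None of it removes the asymmetry.

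A reader might also infer more than the text supports:

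- *That the remdesivir arm is free of events until the first dose.* Only death is impossible before dosing in those retained. A patient with an SAE before the first infusion who is then dosed stays in the set, and section 9.1.7 has that event recorded.
- *That every comparable control is kept.* Controls also need post-baseline safety information, and patients who leave the whole study are not reported on in either arm (section 6).
- *That the protocol prescribes this set for the mortality comparison.* Section 10.5.3 names no population. Its use is inferred from section 10.3, which gives the set no other purpose.
- *That the bias always favours remdesivir.* If the never-dosed are well patients who decline or go home, it runs the other way.

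**Conclusion.** The point holds as a defect in a rule the protocol fixes. The safety population conditions one arm on a post-randomisation event and cannot do so in the other. If the section 10.5.3 endpoints are compared in it, the comparison is selective. Neither the direction nor the size can be stated beforehand: under the assumed 1–5% never dosed, the null RR for death runs from slightly above 1 to about 0.82 in the scenarios relied on, and is exactly 1.00 when never-dosed patients have average mortality. The range rests on assumed values of *u* and *d* and on 5% as a stand-in for three-month mortality.

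The documents do not support saying that the plan conceals deaths in general, since in-hospital and 28-day mortality are also analysed by ITT. The exposed results are mainly three-month death, SAEs, severe AEs and the composite. The matter deserves correction because the remedy costs almost nothing, not because a large bias has been shown.

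**What to change.** In sections 10.3 and 10.5.3, state that between-arm comparisons of death through three months, SAEs and the composite are made primarily in all randomised patients, by allocated arm, with time counted from randomisation. Keep the dosed-only set as a supporting analysis and for descriptive tables of AEs under treatment, including the grade 1–2 reactions during or within an hour of infusion, which exist only for remdesivir. For severe AEs reported alone, name the set and show both. Carry the same wording into the SAP.

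The cost is a wording change in two sections. Collection already starts at consent in both arms, and the change can be made before database lock, while the study statistician is blind to allocation (section 10.2.2). The downside is some dilution: a drug-related excess among dosed patients is multiplied by 1 − u, that is 0.98 with 2% never dosed and 0.95 with 5%. The retained dosed-only analysis addresses this.

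The change does not touch a separate asymmetry: the composite as listed includes discontinuation of study infusions, which standard-care patients cannot have.
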